## 12. DATA AND SAFETY MONITORING

This study is a single site study employing FDA approved medications for an FDA approved indication. Furthermore, the study is of short duration and does not involve vulnerable populations. Therefore, it is considered low risk and in discussions with the NAIMS program officer requires a safety monitoring committee but not an external DSMB. Our proposed safety monitoring plan for this study consists of:

- i. Continuous, close monitoring by the Principal Investigator in conjunction with a named Safety Officer during the first meetings of a Safety Monitoring Committee (see below); and
- ii. Twice yearly meetings of a Safety Monitoring Committee (SMC).

There will be prompt reporting of all adverse events to the Safety Officer as well as prompt reporting of unanticipated problems, serious adverse events as well as other risk-related events to the Columbia University Medical Center IRB, in accordance with their reporting policy. This plan is deemed appropriate because study drugs are FDA approved and are used for FDA approved indications; it does not involve high risk or vulnerable populations; and it is a single site study of short duration.

The Safety Officer and Safety Monitoring Committee (SMC) will act in an advisory capacity to monitor patient safety and evaluate the efficacy of the interventions described in this study.

### Safety assessments

Toxicity monitoring, joint examination, general clinical examination vital signs (including blood pressure) will be assessed at every visit. In between Study Visits I and II patients will return every 6 to 8 weeks for safety visits per standard of care and which will be focused on toxicity monitoring. Interim safety visits will include the following laboratory assessments: CBC with differential, comprehensive metabolic panel, CRP, and ESR. An exit safety visit will take place approximately 8 weeks after the completion of study visit II and the evaluations mentioned above will take place as well. Study visits including radiation exposure (PET-CT, DEXA, x-rays) will include a urine pregnancy test for all female participants of childbearing potential. Disease activity will be evaluated using the CDAI score at the time of every safety and study visit and treatment will be escalated according to standard of care until they reach the state of low disease activity or remission as defined by a CDAI score of less than or equal to 10.

A copy of the Safety Visit Check Off Sheet is attached as Appendix XXVIII.

### Definitions of Adverse Events

An adverse event is any undesirable sign, symptom or medical condition occurring after starting study drug (or therapy). Medical conditions/diseases present before starting study treatment are only considered adverse events if they worsen after starting study treatment.

A serious adverse event is an undesirable sign, symptom or medical condition which: (1) is fatal or life-threatening, (2) required or prolonged hospitalization, (3) results in persistent or significant disability/incapacity, (4) constitutes a congenital anomaly or a birth defect, (5) is medically significant, in that it may jeopardize the subject and may require medical or surgical intervention to prevent one of the outcomes listed above.

In this study, we will utilize a mild, moderate, and severe scale to grade adverse events.

- Mild adverse events will include common side effects with these and other medications, transient laboratory test alterations; discomforts noted but no disruption of daily activities; no therapy, or only symptomatic therapy required.
- Moderate adverse events will include persistent mild events that cause significant impairment in quality of life, laboratory test alterations indicating injury without long-term risk; discomfort sufficient to modify normal daily activity; specific therapy required (i.e. more than symptomatic).

- Severe adverse events prompting immediate withdrawal from the study include laboratory test indicating a serious health threat or permanent injury; incapacity, inability to work, inability to perform normal daily activity; hospitalization required or prolonged; emergency treatment required; life-threatening events; death.

An "unanticipated problem" is any incident, experience or outcome during the study that:

- is serious adverse event or suggests that the study may be placing subjects at a greater risk of harm than was previously known or recognized, and
- is related or possibly related to participation in the research and
- is unexpected given the study procedures and the characteristics or the subject population being studied

All unanticipated problems will be reported promptly to the IRB. All unanticipated problems will also be reported to the safety officer, the SMC, and the funding source for this study (NIH/NIAMS).

In addition all adverse events regardless of whether they constitute unanticipated problems as well as adverse events thought to be related or possibly related to study procedures will also be reported to IRB and to the safety officer, the SMC, and the funding source for this study (NIH/NIAMS).

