## 2. STUDY DESIGN AND STATISTICAL PROCEDURES

### 2a. Study Design

(this section includes references)

For aim 1, the proposed studies will be performed in 150 patients with RA and 15 subjects without RA who will function as controls. The 150 patients will be recruited from the rheumatology clinics at New York Presbyterian Hospital of the Columbia University. The 15 control subjects will be recruited from the internal medicine clinics at the same institution or among friends of the recruited RA patients.

The 150 participants should have RA fulfilling established diagnosed criteria and not have a history of cardiovascular disease as indicated in the section for inclusion/exclusion criteria

[figure not shown]
These patients (150) will undergo the evaluations shown in the table below - and in more detail in Appendices I, II and III - during an initial visit (Visit I).

Evaluations	Visit I September/2011 - August/ 2014
Cardiac PET-CT scan*	X
3D Echocardiogram & CV Questionnaires	X RA X
Joint examination	X
Phlebotomy	X
Anthropometry	X
DEXA scan (body composition)**	X

\*including 3 transverse CT slices (mid-chest, L4-L5, mid-thigh) and cardiac CT for evaluation of coronary artery calcification (CAC).

\*\*only for the 50 participants who will be recruited for aim 2. (see below)

During the first PET scan a cardiac CT scan will be obtained in order to quantify coronary artery calcium (Agatston Score). Three additional CT Slices will be obtained (mid chest, lumbar, and mid thigh) to evaluate for visceral fat

accumulation as a risk factor for cardiovascular disease.

Controls will undergo only the PET-CT scan, 3D Echo, anthropometry evaluations, phlebotomy, and will complete abbreviated cardiovascular related questionnaires as outlined in Appendices I, II and III.

The PET-CT scan will occur on the same day or within one week of Study visit I.

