After the escalation in their treatment at baseline (Study Visit I) these patients will return for a second (24 weeks) study visit respectively and the set of evaluations shown in the table below - and in more detail in Appendices I, II and III - will take place. A window of +/- 2 weeks will be allowed in scheduling the study visits.

Visit II	
Evaluations	Mar/2012-Jan/2015
Cardiac PET-CT scan*	X
3D Echocardiogram	X RA &
CV Questionnaires	X
Joint examination	X
DEXA scan (body composition)	X
Phlebotomy	X
Anthropometry	X

\*including 3 transverse CT slices (mid-chest, L4-L5, mid-thigh) and low dose radiation chest CT

During PET-CT scans a low dose CT imaging of the chest is always obtained for attenuation correction as part of the usual PET-CT protocol. Although we will not need a repeat coronary artery calcium score at visit 2, low dose radiation CT imaging of the chest is always obtained for attenuation correction as part of the usual PET protocol. During this CT imaging acquisition 3 additional slices (CT cuts) will be again obtained (mid chest, lumbar, and mid thigh) to evaluate for change in visceral fat following treatment initiation.

The 3-dimensional Echocardiogram (3D Echo) will be performed to provide a measure of LV mass and will be performed in every study visit.

The 15 controls will also be asked to have a repeat set of evaluations 6 months (24 +/- 2 weeks) after their first evaluation without any therapeutic or other intervention in between the two visits. The inclusion of non-RA controls will provide important data on the normal variation of cardiac PET-CT and 3D Echo parameters over time. Further evaluations for the control participant visits are outlined in appendices I, II and III.

Every subject (RA patient or non RA control) will have a urine pregnancy test prior to tests involving radiation exposure (PET-CT scan and DEXA) and on the same day.

The screening and consent process of a patient to receive randomized escalation of treatment will be made at the time they are consented for the first study visit. It is possible that all 150 patients will qualify for randomization of their treatment but only the first 50 of those will be selected to return for study visit II. The rest of the patients will exit the study and will continue their regular care with escalation of their treatment by their treating rheumatologist outside the study.

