#### PET Imaging Protocol:

PET utilizes radiolabeled agents (such as  $[^{13}\text{N}]$  ammonia) for the measurement of myocardial blood flow at rest and during pharmacological stress using agents such as the vasodilator adenosine. The percent increase in blood flow from

rest to stress provides a measure of coronary blood flow reserve, including microvascular flow. Normal subjects without cardiovascular disease or risk factors have a coronary flow reserve on the order of 4. They are capable of a 4 fold increase in blood flow with pharmacological stress, while patients with coronary artery disease demonstrate attenuations in coronary flow reserve.

We will perform PET myocardial perfusion imaging using [N] ammonia for the measurement of myocardial blood flow at rest and during pharmacological stress using the vasodilator adenosine. PET imaging will be performed in a blinded procedure in all subjects under the supervision of [name], Investigator and Director of the Columbia University Medical Center Cardiac Positron Emission Tomography Center. [name] will otherwise have no contact with the study subjects and will not be aware of participants' clinical info collected during the study. The PET data will be acquired on the Siemens Biograph Truepoint 40 PET/CT scanner. The camera has 4mm resolution and scan time performance superior to the prior generation of PET imaging devices. The Siemens biograph uses computed tomography (CT) acquisition for attenuation correction as well as co-registration with the emission image. PET data are collected in 47 planes 3.375 mm thick that cover a range of 16 cm. A dose of 10 mCi of [N] ammonia is injected and a 10 min dynamic acquisition is started. The process is repeated, including a second attenuation scan, for the stress study. The injections of ammonia are separated by at least 40 minutes to allow the first injection to decay to a level where it will not interfere with the second study. All scanning is performed in 2D gated mode and reconstructed with filtered back projection using a Hann filter cutoff at 1 cycle/cm.

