## 6. STUDY SUBJECTS

(this section includes references)

Subjects fulfilling the 2010 ACR-EULAR diagnostic criteria for RA (1) but without any history of previous self reported or physician diagnosed cardiovascular events will be eligible for participation in the study. The goal is to

enroll 150 patients for the purposes of this protocol. Subjects will be recruited from the arthritis clinics at the Columbia University.

Among the subjects above, patients with RA who have moderate to high disease activity as defined by a CDAI higher than 10 will be given the opportunity to consent for randomization in treatment with either a TNF inhibitor or alternative treatment and return for follow up visits as indicated in earlier sections. 50 patients will be randomized to this aspect of the study.

15 subjects without RA and without prior cardiovascular disease will also be recruited. These subjects will be recruited among patients in the internal medicine clinics at the Columbia University or from friends of the recruited patients.

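### The adverse-event definition starts at study drug, so it leaves out 115 of 165 participants who have research PET-CT without ever taking study drug, and it conflicts with the protocol's own rule on reporting procedure-related events

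*Combined protocol and SAP*

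**What the plan says.** Section 12, Definitions of Adverse Events, sets the start of the window: "An adverse event is any undesirable sign, symptom or medical condition occurring after starting study drug (or therapy"). The next sentence counts a pre-existing condition only if it worsens once study treatment has begun. No other window is given.

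The reporting paragraph that closes the same section sends two groups of events to the IRB, the safety officer, the Safety Monitoring Committee (SMC) and the funder. The first is all adverse events, whether or not they are unanticipated problems. The second is "adverse events thought to be related or possibly related to study procedures".

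Section 2a sets out who is studied: "For aim 1, the proposed studies will be performed in 150 patients with RA and 15 subjects without RA who will function as controls". Section 6 limits treatment allocation: "50 patients will be randomized to this aspect of the study". Of the other RA patients, section 2a says: "The rest of the patients will exit the study and will continue their regular care". Controls are scanned twice, about six months apart, with no treatment in between: "Controls will undergo only the PET-CT scan, 3D Echo, anthropometry evaluations, phlebotomy", plus short questionnaires.

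Section 3, PET Imaging Protocol, describes perfusion imaging "at rest and during pharmacological stress using the vasodilator adenosine" and adds: "PET imaging will be performed in a blinded procedure in all subjects". Section 3 lists PET-CT among the procedures that are not part of usual care. Section 11 attributes PET-CT mortality, which it calls low, mainly to the adenosine stress phase.

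**The concern.** The definition follows the part of the study that the protocol treats as ordinary care and misses the part done only for research. Section 13 describes the treatment as what patients would receive anyway. The adenosine stress test and the radiation are what the study adds, and most people exposed to them never start a study drug.

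The reporting rule for procedure-related events does not clearly repair this, because it uses the term that the definition has just restricted. Read literally, a reaction during a control's scan is not an adverse event, so the rule has nothing to act on. Read generously, such a reaction reaches the SMC only after someone judges it at least possibly related, whereas events after drug start are reported whatever their cause. The SMC is asked to weigh participant risk against benefit, and it would do so with complete counts for the drug phase and selective counts for the imaging phase.

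**Working it through.** The plan gives no figure to reproduce. The check is a head count from planned numbers, without dropout, followed by a comparison of the reporting routes.

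**People**
- RA patients: 150; controls: 15 (section 2a). Total = 150 + 15 = 165.
- Randomized to study treatment: 50 (section 6).
- Never on study drug = 165 − 50 = 115, that is, 100 RA patients and 15 controls.
- Share = 115 / 165 = 69.7%.

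**PET visits**
- First scans: 165. Second scans: 50 randomized RA patients and 15 controls (section 2a). Total = 165 + 50 + 15 = 230.
- Outside the definition in every case: 100 scans in aim-1-only RA patients + 15 × 2 control scans = 130. Share = 130 / 230 = 56.5%.
- Outside it only if done before the first dose: the 50 baseline scans of randomized patients. With all of them, 130 + 50 = 180. Share = 180 / 230 = 78.3%.

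The documents do not settle where in this range the study falls. Section 2a puts treatment escalation at Study Visit I and allows the PET-CT on that day or up to a week from it. Section 6 lets the Visit I echocardiogram exclude patients with a low ejection fraction, which suggests imaging first, but that concerns the echocardiogram and not the PET.

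**Which events have a route when the participant has not started study drug**

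| Event | Route in section 12 | Covered? |
|---|---|---|
| Serious reaction | The serious adverse event definition has no drug-start condition of its own | Probably yes |
| Unanticipated problem | Covers the whole study; needs potential for greater harm, relatedness and unexpectedness | Yes, if all three are met |
| Non-serious, expected procedure reaction | Neither serious nor unanticipated; only the procedure clause remains | Only if adverse event is read more widely than defined |
| Non-serious event not judged related | None | No |

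**Can study drug mean adenosine?** Section 4 lists only TNF inhibitors and other medicines given for RA care. Neither adenosine nor the PET tracers appear, and the parenthetical mention of therapy is not explained. Nothing in the text supports stretching the term to imaging agents.

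**The case against.** The strongest reply is that the reporting paragraph names procedure-related events separately from all adverse events. That second group adds little unless it reaches beyond the drug phase, so the natural reading is that procedure reactions in any participant go to the SMC. The threshold is only possible relatedness, which a reaction during an adenosine infusion would readily meet. The opening of section 12 also sends other risk-related events promptly to the IRB, and the SMC is to discuss adverse-event reporting before the study begins. Section 11 gives reasons to expect few serious events: it reports no deaths in over 11000 stress tests at the centre and excludes people with risk factors for stress complications. No endpoint or efficacy analysis is affected.

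Much of this stands. A reader might infer from the definition that nothing happening to the 115 would ever be reported. The documents do not support that, because serious events and unanticipated problems are described without reference to drug start and the procedure clause shows that the authors meant procedure events to count. A reader might also take 78% as the share of scans left out. That is only the upper end, and both percentages are shares of scans under a literal definition, not shares of events that would go unreported.

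What the reply does not remove is the conflict itself. The procedure clause covers people without study drug only if its key term is given a meaning that the definition denies. Even then, it passes on only events that someone has judged related.

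**Conclusion.** The point holds as a conflict within section 12 with a limited practical gap. On its wording, the adverse-event definition excludes 115 of 165 participants (69.7%) and 130 to 180 of 230 planned PET visits (57% to 78%). The head count rests only on the planned numbers. The scan range also depends on the unstated order of baseline PET and first dose, and assumes that everyone attends.

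The events exposed are mainly non-serious, expected reactions to study procedures, and non-serious events not judged related, in people who have not started study drug. It would go too far to say that these participants have no safety reporting. The documents give no rate for non-serious reactions, so the number of events at risk of being missed cannot be estimated. The correction is worth making because the affected group is most of the study, the procedure is the main research-only exposure, and the change is small.

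**What to change.** In section 12, Definitions of Adverse Events, start the adverse-event window at consent or first study procedure for every participant, controls included, and end it at that participant's last study contact. Align the sentence on pre-existing conditions with the same starting point. The reporting rule for procedure-related events then uses a term that covers the people it is meant to cover, and the order of baseline PET and first dose no longer decides whether a reaction counts.

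The cost is one revised definition and slightly more event recording at imaging visits. No dose, procedure or clinical rule changes. Showing procedure-phase and treatment-phase events in separate tables would help the SMC read the counts, but it is optional.

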Standard of care entails that patients who undergo escalation of their treatment need to be evaluated every 6-8 weeks to evaluate response to treatment, the need for further treatment escalation, and toxicity monitoring. Thus in between Study Visits I and II patients will return every 6-8 weeks for safety visits which will mirror standard of care management and which will be focused on toxicity monitoring as it would happen even if the patients did not participate in the study. An exit safety visit will occur 6-8 weeks after visit II. The incorporation of safety visits in the study and the related procedures/tests are shown in Appendices I and II.

It is possible that patients randomized to receive either the triple therapy or treatment with a TNF inhibitor and methotrexate may not respond to treatment. Disease activity will be evaluated using the Clinical Disease Activity Index (CDAI) score at the time of every safety and study visit and treatment will be modified until they reach the state of low disease activity or remission as defined by a CDAI score of less than or equal to 10. CDAI score takes into account the number of swollen and tender joints and the evaluation (using a Visual Analog Scale) of disease activity by both the patient and the physician. CDAI is an extensively validated disease activity tool.

[figure not shown]
The treatment algorithm followed in this study is described below. A study flow chart describing the algorithm is provided in appendix XXI.

i. Randomization to the non TNF inhibitor arm: Patients on triple therapy will be started on 1 gram of sulfasalazine (SSZ) twice daily along with weight adjusted daily Hydroxychloroquine (Plaquenil). Methotrexate treatment will be continued. It takes approximately 6 weeks before an effect of this therapeutic regimen is experienced. In the first safety visit (which will happen approximately 8 weeks after the first study visit) the need to increase the SSZ to 3 grams daily will be evaluated based on whether the patient has reached low disease activity status or remission. In the subsequent safety visit (safety Visit 2) which will occur 8 week after Safety Visit 1, if disease activity remains moderate or high, SSZ and Hydroxychloroquine will be stopped and patients will be switched to Leflunomide (Arava) 10 mg plus methotrexate.

Patients will then return at 24 weeks for their second Study Visit (Study Visit 2) for completion of the study and further management as per standard of care.

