An additional Safety Visit (Safety Visit 3) will take place at 32 weeks and will serve as an exit safety visit.

ii. Randomization to the TNF inhibitor arm: For patients randomized to receive treatment with a TNF inhibitor, disease activity will also be evaluated at the time of every visit. The effect of TNF inhibitors on arthritis activity may be observed as early as in 2 weeks but sometimes may take up to 14 weeks (approx. 3 months). At the time of the first safety visit tolerability and safety will be evaluated. At the time of Safety Visit II if CDAI is still >10 (indicative of moderate disease activity) an increase in the dose or frequency of the TNF inhibitor (in the case of agents such as infliximab or adalimumab where escalation of dosage is an option) or a switch to treatment to an alternative TNF

inhibitor will take place.

Patients will then return at 24 weeks for their Second Study Visit (Study Visit 2) for completion of the study and further management as per standard of care.

An additional Safety Visit (Safety Visit 3) will take place at 32 weeks and will serve as an exit safety visit.

The treatment algorithm described above is similar to the care patients would receive even if they did not participate in the study. The only difference is that patients will be randomized to receive one of the two standard of care treatments. The need for prednisone to temporarily control disease activity will be decided by the investigators according to usual standards of care.

As already mentioned decisions to escalate treatment will be based on CDAI score which is a composite disease activity score consisting of counts of swollen and tender joint counts and evaluation of disease activity by both the patient and the physician using a visual analog scale. The joint counts will be performed by a blinded trained joint assessor. Either a faculty member or a senior rheumatology fellow, also not aware of the patient treatment will perform the joint examinations and the assessment of disease activity. The same joint assessor will perform the joint counts for a given patient throughout the study. Every time CDAI is  $>10$ , then a change in the treatment according to the algorithm described above will be mandated to ensure patients' well being.

[figure not shown]

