Linear mixed effects (MIXED) regression models will be used to assess trends in LV structure and functional outcomes over time between the two visits for the patients who will undergo randomization reevaluation with PET-CT and 3D Echocardiogram, while controlling for potential confounders. The data will include PET-CT studies for 25 RA patients receiving TNF antagonists and 25 RA patients receiving alternative treatment, and PET-CT studies for 15 non-RA patients. The data are longitudinal since LV outcomes are measured for each person at 2 different time points. Since repeated measures tend to be correlated within a person, mixed models with both fixed and random effects will be used to adjust for this correlation. We will use unstructured correlation structure given that each visit will occur roughly around a fixed time since study visit I, and use robust standard error estimates to conduct statistical inferences. To study the TNF inhibitor effects on LV structure or functional outcomes, visit-specific indicators, RA status, TNF treatment status, and visit x TNF treatment interaction will form the bases for the mean model. The visit-specific indicators will capture the time trend of LV outcomes over the study period, the RA status will delineate the overall mean difference in LV outcomes between RA and non-RA, with the TNF treatment status indicator and its interaction with visit indicators capturing the baseline difference in LV outcomes between TNF treated and non-treated groups and the potential TNF treatment effect on LV outcome over time, respectively. Actual TNF inhibitor dosage could be used in place of TNF status indicator in the model if necessary, and other potential covariates could be added into the model for confounding adjustment. For example, inflammation markers could be added into the model to examine whether any TNF treatment effect is mediated through the change in systemic inflammation. Similar modeling approaches can be used to study all research questions of interest using the corresponding outcomes and their hypothesized predictors listed in those questions to be addressed. For any binary outcomes in this type of regression analysis, e.g. indicator of whether a LV outcome exceeding certain critical value, generalized linear mixed effects models (GLIMMIX) can be used to study the odds of such outcome as a function of the independent variables.

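### Severe adverse events are tied to withdrawal from the study rather than from treatment, which, if followed, forfeits the only post-baseline imaging

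*Combined protocol and SAP*

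**What the plan says.** Two parts of the plan bear on a randomized patient who becomes seriously unwell before week 24.

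**Section 12, *Definitions of Adverse Events*.** A disease present at baseline can become an adverse event: "Medical conditions/diseases present before starting study treatment are only considered adverse events if they worsen after starting study treatment". RA is not exempted. The third level of the grading scale opens with "Severe adverse events prompting immediate withdrawal from the study include laboratory test indicating a serious health threat or permanent injury" and goes on to list "incapacity, inability to work, inability to perform normal daily activity; hospitalization required or prolonged; emergency treatment required", then life-threatening events and death.

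**Section 2a (treatment algorithm) and section 12, *Safety assessments*.** Each time the CDAI is above 10, "then a change in the treatment according to the algorithm described above will be mandated". The safety section repeats the rule: "treatment will be escalated according to standard of care until they reach the state of low disease activity or remission". Neither states a severity above which it ceases to apply. After any switch, the triple-therapy arm is told: "Patients will then return at 24 weeks for their second Study Visit (Study Visit 2) for completion of the study". The TNF inhibitor arm has the same instruction in almost the same words.

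**Outcome schedule.** Section 2a says of the randomized patients that "these patients will return for a second (24 weeks) study visit respectively", with a window of 2 weeks either side. On the aim 2 analysis it says: "The data are longitudinal since LV outcomes are measured for each person at 2 different time points".

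**The concern.** A disabling flare can meet the severe-grade terms (incapacity, inability to work, hospital admission). For that patient, section 12 points to leaving the study, while section 2a points to changing treatment and returning at week 24. No sentence in the supplied text says which governs. Drug toxicity of the same grade also points to leaving the study, and for it there is no competing instruction at all. Nothing in the text separates stopping a drug from leaving the study, or arranges imaging for someone who has stopped.

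With only two measurement times, a patient withdrawn before Visit II has no 24-week change in LV mass, function, perfusion or FDG uptake. Both the course of RA and drug toxicity can depend on the assigned treatment, so these values would be missing for a reason that may be related to treatment, in an open-label comparison of 25 per arm. One of the aim 2 questions in section 2a relates change in RA activity to change in myocardial perfusion and inflammation. Losing the patients with the worst RA course would remove one end of that range.

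**Working it through.** **Step 1. The same patient under each rule**

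| Situation before week 24 | Section 12 definitions, read literally | Section 2a and *Safety assessments* |
|---|---|---|
| CDAI above 10, not severe grade | No withdrawal | Change treatment, return at week 24 |
| RA worsening that reaches severe grade | Immediate withdrawal from the study | Change treatment, return at week 24 |
| Drug toxicity that reaches severe grade | Immediate withdrawal from the study | No specific rule on follow-up |

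The rules conflict in the second row. The third row has no conflict, but Visit II is exposed in the same way.

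**Step 2. Inputs for the precision cost (section 2b)**
- 25 patients per arm; 15% drop-out; two-sided alpha 0.05; power 80%.
- Stroke volume (SV): SD 4.2 mL/m²; correlation between visits 0.2.
- Plan's figure: detectable within-arm change 3.42 mL/m², stated for N=22.

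**Step 3. Reproduce the plan's figure**
- SD of change = 4.2 × √(2 × (1 − 0.2)) = 4.2 × √1.6 = 5.31.
- Patients left after drop-out: 25 × 0.85 = 21.25.
- Paired t-test, noncentral t: detectable change = d × 5.31, where d is the standardized change giving 80% power.
- N=22: d = 0.626, giving 3.33. N=21: d = 0.643, giving 3.41.

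The printed 3.42 agrees with N=21 to within rounding, so N=21 is the baseline below.

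**Step 4. Withdrawals within the allowance**

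The allowance is 25 × 0.15 = 3.75 patients per arm. Severe-event withdrawals that fall inside it are already counted, so they add no precision cost. One withdrawal is 1/25 = 4% of an arm.

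**Step 5. Withdrawals on top of the allowance**

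The documents give no rate, so one and two extra losses, both in the TNF inhibitor arm, are assumptions for illustration. The between-arm rows use a two-sample t-test and further assume an SD of change of 5.31 in both arms.

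| Comparison | N | d | Detectable SV change (mL/m²) | Increase |
|---|---|---|---|---|
| Within TNF arm | 21 | 0.643 | 3.41 | – |
| | 20 | 0.660 | 3.51 | 3.51/3.41 = 1.03, about 3% |
| | 19 | 0.680 | 3.61 | 3.61/3.41 = 1.06, about 6% |
| Between arms | 21 v 21 | 0.886 | 4.71 | – |
| | 20 v 21 | 0.898 | 4.77 | 4.77/4.71 = 1.013, about 1% |
| | 19 v 21 | 0.910 | 4.84 | 4.84/4.71 = 1.03, about 3% |

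Power is therefore not the issue. What matters is an avoidable loss of 24-week values for reasons that may be tied to treatment.

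**The case against.** **The bullet may only describe a grade.** It sits in a list of definitions, and that list ends with death, which cannot operate as a withdrawal instruction. It could also mean only those severe events that happen to prompt withdrawal. Both readings are possible. Neither gives the investigator another test for who leaves, and a withdrawal rule with several readings should be clarified.

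**The RA algorithm is the more specific rule.** It covers uncontrolled RA, allows temporary prednisone at the investigators' discretion, and comes with visits every 6 to 8 weeks. It is reasonable to let it take precedence for RA, but no sentence says so, and it does not help a patient with severe drug toxicity.

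**Other material may settle it.** Appendix XXI (algorithm flow chart) and Appendix XXVIII (safety visit check-off sheet) are not in the supplied text. *Committee Process* puts adverse-event reporting and stopping rules on the agenda of the safety committee's first meeting. Either might address individual withdrawal, but the text does not show that either does.

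**Loss of Visit II is inferred.** This is correct. It follows from the words about leaving the study and from the absence of any provision for imaging afterwards. The plan does not state it outright.

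**The numerical effect is slight.** This is also correct. Even the largest figure above, 4.84 mL/m², is well below the pilot change of 12.5 mL/m² cited in section 2b.

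**A remedy limited to RA would be too narrow.** An exemption for RA worsening without suspected toxicity would leave the gap open for toxicity and would make retention depend on an unblinded judgement. This objection stands, and the fix below applies whatever the cause.

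**Conclusion.** The point holds as a cheap improvement of minor severity. The plan ties severe adverse events to leaving the study. If that wording is followed, any randomized patient with such an event before week 24 loses the only post-baseline PET-CT and echocardiogram, for a reason that may depend on treatment. This rests on the literal reading of the severe-grade bullet and on the inference that a withdrawn patient does not attend Visit II. The number of patients affected cannot be derived and may be zero. The precision cost is nil within the 15% allowance. For one or two losses beyond it in the TNF inhibitor arm, it is about 3% or 6% within the arm and 1% or 3% between arms.

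A reader might infer more than the documents support:
- *That every non-responder is withdrawn.* A patient whose CDAI merely stays above 10 without reaching the severe grade falls only under the treatment algorithm.
- *That the treatment comparison is biased in a known direction.* Neither the rate of severe events nor its split by arm is given, so no direction can be stated.
- *That the patient drops out of the analysis.* The mixed model in section 2a can still use the baseline value. What is lost is the 24-week measurement.

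**What to change.** Amend the severe-grade bullet in *Definitions of Adverse Events* along these lines:

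> A severe adverse event leads to stopping or changing study treatment as clinically needed. It does not by itself lead to withdrawal from the study. Worsening of RA continues to be managed under the CDAI algorithm. Visit II imaging at 24 (+/- 2) weeks is still done for every randomized patient, whatever the reason for stopping treatment, unless the patient declines or it is unsafe, including adenosine stress. All such events are still reported as adverse events.

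Appendices XXI and XXVIII should be checked for agreement with this wording.

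The cost is a few sentences of protocol text, with no new visits or tests. The downside is that an unwell patient is asked to attend an imaging visit, which may be declined, and the investigator must judge whether the stress scan is safe. Because the rule does not depend on the cause of the event, retention does not turn on an open-label judgement about drug toxicity.
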